3.2. Endpoints

3.2.1. Primary Endpoints

- General safety variables: Adverse event (AE) assessments, clinical laboratory tests (hematology, clinical chemistry, coagulation and urinalysis), vital signs (blood pressure [BP], pulse, tympanic temperature and respiratory rate [RR]), 12-lead electrocardiogram (ECG), physical examinations
- Specific safety variables: Injection site assessments, immunogenicity assessments (ADA, NAb, anti-PEG) (performed only if analysis is necessary)

3.2.2. Secondary Endpoints

- C_{max} : Maximum serum HM15912 concentration determined from the concentration-time profile
- T_{max} : Time of maximum serum HM15912 concentration determined from the concentration-time profile
- AUC_{0-t} : Area under the concentration-time curve from predose (time 0) to the last quantifiable concentration
- AUC_{inf} : Area under the concentration-time curve from predose (time 0) extrapolated to infinite time ($AUC_{0-t} + C_{last}/\lambda_z$) calculated using the linear-log trapezoidal rule
- $AUC_{\%extrap}$: Percentage of AUC_{inf} that is due to extrapolation beyond t_{last}
- λ_z : The terminal elimination rate constant determined by selection of at least 3 data points on the terminal phase of the concentration-time curve
- $t_{1/2}$: Terminal elimination half-life calculated as: $\ln 2/\lambda_z$
- CL/F : Total body clearance calculated as: Dose/ AUC_{inf}
- V_z/F : Apparent volume of distribution calculated as: Dose/($AUC_{inf} * \lambda_z$)

3.2.3. Exploratory Endpoints

- Blood plasma citrulline
- Albumin, prealbumin
- Fasting lipid panel (total cholesterol, triglycerides, low-density lipoprotein [LDL], high-density lipoprotein [HDL], very low-density lipoprotein [VLDL], free fatty acid [FFA])
- Blood glucose-related panel (fasting plasma glucose, gastric inhibitory polypeptide [GIP], glucagon-like peptide-1 [GLP-1], C-peptide, glucagon, insulin)
- Insulin-like growth factor-1 growth factor-1; IGF-1) and keratinocyte growth factor (KGF)

3.3. Rationale for the Study Design

This study evaluates the safety, tolerability, PK and PD of single ascending doses of HM15912 administered via SC injection. This study was designed to minimize bias and to obtain reference data (i.e., data from placebo-treated subjects) which will aid in the interpretation of results through double blind and placebo control.

For this FiH study, sentinel dosing will be utilized for each cohort. This will minimize the number of subjects affected by rapid side effects after HM15912 administration. The Principal Investigator and the Sponsor will review available blinded safety and tolerability data after each cohort to determine the next dose and then decide whether the dose escalation should be stopped or whether the dose should be increased/decreased in the subsequent cohort. If PK/PD data have been obtained, they can be used for reference. This is not mandatory, however.

The planned safety assessments that will be performed during the study are measures for ensuring the safety of subjects during a clinical trial. The PK sampling schedule is considered appropriate given the information obtained from the nonclinical study results of HM15912. The rationale for dose selection is discussed in Section 5.2.

Based on the in vivo effect of endogenous GLP-2, the exogenous administration of HM15912, a GLP-2 analogue, is expected to expand the mucous epithelium of the small intestine and colon resulting from the proliferation of crypt cells¹. Plasma citrulline is a nonprotein amino acid that is mostly synthesized in the small intestine cells, and is well-known as a noninvasive plasma biomarker for intestinal cell mass². Apolipoprotein AIV is also mostly synthesized in the small intestine cells, and previous studies have shown the correlation between apolipoprotein AIV and plasma citrulline levels³. Therefore, effect of HM15912 on expansion of the intestinal mucous membrane will be explored by measuring plasma citrulline after HM15912 administration. The serum proteins, albumin and prealbumin, and serum lipid panel will also be evaluated to observe changes in nutrient status of subjects resulting from expansion of the intestinal mucous membrane⁴.

GLP-2 affects the pancreas and is involved in the secretion of glucagon and maintenance of glucose homeostasis¹. These pancreatic hormones are balanced in a physiological condition, and this study will explore the effect of GLP-2 administration on the homeostasis.

3.4. Dose Escalation and Study Stopping Criteria

Dose escalation will be stopped if 1 of the following conditions applies:

- Death of a subject in 1 cohort, at any time, that is considered to be related to the IP, judged by the Principal Investigator
- One or more of the subjects in 1 cohort have experienced serious AE that is considered to be related to the IP, judged by the Principal Investigator.
- Two or more of the subjects in 1 cohort have experienced severe AE that is considered to be related to the IP, judged by the Principal Investigator.
- Two or more of the subjects in 1 cohort have experienced moderate AEs that persist for more than 7 days and are considered to be related to the IP, judged by the Principal Investigator.
- Two or more of the subjects in 1 cohort develop similar clinically significant laboratory, significant ECG or vital sign abnormalities, or severe AEs in the same organ class,

indicating dose-limiting intolerance. Dose escalation may proceed if after review of the data by the Principal Investigator and discussion with the Sponsor, it is concluded that the events are not drug related.

- It is determined that the limit of safety and/or tolerability has been reached. Decision will be made between the Sponsor and the Principal Investigator.

If any delayed reactions occur in subjects administered HM15912 during this study, the Principal Investigator will immediately stop the administration and take appropriate medical measures. If delayed reactions are suspected to be drug hypersensitivity reactions, appropriate medical measures will be taken in accordance with 7.9. Handling of Hypersensitivity Reactions. If Principal Investigator and Sponsor discuss and agree that administering HM15912 to other subjects is an unacceptable risk, they may stop the study as below.

The Principal Investigator and the Sponsor may stop the clinical study after an appropriate discussion if conditions or events including, but not limited to, the following occur during the study. A sufficient written statement on the reason for stopping the study will be submitted to the IRB.

- If clear risks or unacceptable risks are found in the subjects enrolled in this clinical study
- If the Sponsor decides to postpone or stop development of the IP

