4.1. Number of Subjects

A total of approximately 40 subjects will be enrolled in the clinical study (N = 8 per cohort with 6 randomized to HM15912 and 2 randomized to matching placebo within each group) according to the inclusion/exclusion criteria. Enrolling 8 subjects per cohort (HM15912:placebo=6:2) has been set based on the experience and the general properties of exploratory studies, and this matches the typical sample size used in similar studies conducted to assess safety and PK. Therefore, no formal sample size calculation will be performed (refer to Section 8.11).

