5.2.1. Rationale for Dose Escalation

After at least 6 subjects (HM15912, n ≥ 4) in each cohort have completed assessments through at least Day 17, blinded safety data will be reviewed and a dose decision/dose escalation decision for the subsequent cohort will be made by the Principal Investigator and the Sponsor. If PK/PD data have been obtained, they can be reviewed as well. This is not mandatory, however. The parties will decide about the next dose level taking into consideration the outcome from the blinded safety review, the stopping rules (Section 3.4), and the available PK/PD data.

Depending on the nature, frequency and severity of the safety profile observed in the clinical study, the Principal Investigator and the Sponsor will decide one of the followings. If dose is escalated to 1.5 mg/kg or above or dose is reduced from the planned dose, approval of the MFDS and the IRB will be obtained.

1. Proceed with dose escalation and determine the next higher dose;
2. Stop dose escalation (i.e., no further dosing);
3. Investigate a lower dose level (intermediate between the current and prior ones).

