6.2.1.1.2. Definition of Serious Adverse Event

An SAE is defined as any untoward medical occurrence that at any dose:

- Results in death
- Is life-threatening; this means that a subject was at risk of death at the time of the event; it does not mean that the event hypothetically might have caused death if it were more severe
- Requires inpatient hospitalization or prolongation in existing hospitalization
- Results in persistent or significant disability/incapacity or substantial disruption of the ability to conduct normal life functions
- Is a congenital anomaly/birth defect, or
- Is another important medical event (see below)

Important medical events that do not result in death, are not life-threatening or do not require hospitalization may be considered SAEs when, based on appropriate medical judgment, they may jeopardize a subject and may require medical or surgical intervention to prevent one of the outcomes listed above. Examples of such medical events include allergic bronchospasm requiring intensive treatment in an emergency room or in a physician's office, blood dyscrasias or seizures that do not result in inpatient hospitalization, and the development of drug dependency or drug abuse.

A distinction should be drawn between serious and severe AEs. Severity is a measure of intensity whereas seriousness is defined by the criteria above. For example, a mild degree of gastrointestinal bleeding requiring an overnight hospitalization for monitoring purposes would be considered an SAE, but is not necessarily severe. Similarly, an AE that is severe in intensity is not necessarily an SAE. For example, alopecia may be assessed as severe in intensity but would not be considered an SAE.

Medical and scientific judgment should be exercised in deciding if an AE is serious and if expedited reporting is appropriate.

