6.2.1.2. Recording of Adverse Events

AEs should be collected and recorded for each subject from the date he/she signs the ICF until the end of their participation in the study, i.e., the subject has discontinued or completed the study. If a subject is withdrawn prior to randomization, AEs occurring in him/her will not be

collected.

All AEs and SAEs will be recorded in source documents and, if applicable, in relevant eCRF pages and SAE forms. The Investigator is responsible for reporting AEs or SAEs using medical terms if possible.

AEs may be volunteered spontaneously by a subject, or discovered by the study staff during physical examinations or by asking an open, non-leading question such as "How have you been feeling since you were last asked?" All AEs and any required remedial action will be recorded. The type of AE, date (and time, if known) of AE onset, date (and time, if known) of AE end, severity and action taken of the AE will be documented together with the Investigator's assessment of the seriousness of the AE and causal relationship to IP and/or study procedure.

All AEs should be recorded using standardized medical terms. AEs will be coded using the Medical Dictionary for Regulatory Activities (MedDRA).

6.2.1.3. *Assessment of Adverse Events*

Each AE will be assessed by the Investigator with regard to the categories discussed in the following sections.

6.2.1.3.1. *Severity*

The Investigator will assess all AEs for severity in accordance with the following standard ratings.

- Mild: Ordinarily transient symptoms, does not influence performance of a subject's daily activities. Treatment is not ordinarily indicated.
- Moderate: Marked symptoms sufficient to make a subject uncomfortable. Moderate influence on performance of a subject's daily activities. Treatment may be necessary.
- Severe: Symptoms cause considerable discomfort. Substantial influence on performance of a subject's daily activities. May be unable to continue in the study and treatment may be necessary.

When changes in the intensity of an AE occur more frequently than once a day, the maximum intensity for the event should be noted for that day. Any change in severity of signs and symptoms over a number of days will be captured by recording a new AE, with the amended severity grade, and the date (and time, if known) of the change.

6.2.1.3.2. *Causality*

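### Stopping criteria 3 and 4, read literally, miss one pair: one prolonged related moderate AE plus one prolonged related non-serious severe AE triggers no count-based stop, although two moderate ones do

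*Protocol*

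**What the plan says.** Protocol Section 3.4 lists six conditions, any one of which stops escalation. Numbered in the order listed, the ones that matter here are:

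- **Criterion 2:** "One or more of the subjects in 1 cohort have experienced serious AE that is considered to be related to the IP". One subject is enough.
- **Criterion 3:** "Two or more of the subjects in 1 cohort have experienced severe AE that is considered to be related to the IP". Any duration counts.
- **Criterion 4:** "Two or more of the subjects in 1 cohort have experienced moderate AEs that persist for more than 7 days", with the events judged related.
- **Criterion 5:** two or more subjects with similar clinically significant laboratory, ECG or vital sign abnormalities, or with severe AEs in the same organ class. This one carries an override: "Dose escalation may proceed if after review of the data by the Principal Investigator and discussion with the Sponsor", if they conclude that the events are not drug related.
- **Criterion 6:** the Sponsor and the Principal Investigator decide that the limit of safety or tolerability has been reached. There is no count.

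Two definitions bear on the point. Section 6.2.1.1.2 separates severity from seriousness and notes that "alopecia may be assessed as severe in intensity but would not be considered an SAE". Section 6.2.1.3.1 treats mild, moderate and severe as distinct ratings and adds: "Any change in severity of signs and symptoms over a number of days will be captured by recording a new AE".

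Cohort size is in Section 4.1: "N = 8 per cohort with 6 randomized to HM15912 and 2 randomized to matching placebo within each group". Under Section 5.2.1 the decision on the next dose is made "Depending on the nature, frequency and severity of the safety profile observed in the clinical study".

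**The concern.** A fixed stopping rule should not weaken when one of the events that triggered it gets worse. Here it does. Two subjects with prolonged related moderate AEs oblige the study to stop escalating. If one of those AEs is instead graded severe and is not serious, the moderate count falls to one, the severe count rises only to one, and the obligation disappears.

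This is a first-in-human study in healthy volunteers who have no direct benefit (Section 1.3). What is lost is the mandatory stop: the decision passes to the Principal Investigator and the Sponsor. A safety stop also labels the current dose the minimum intolerable dose and the one below it the maximum tolerated dose (Section 5.2.2). Those definitions stay as they are, but whether the stop is mandatory can affect which dose receives the label.

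**Working it through.** The plan states no error rate or stopping probability for this rule, so there is no figure to reproduce. The check has two parts.

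**1. Logic, from the text alone.** Take a cohort with exactly two affected subjects, each with one related, non-serious clinical AE, moderate or severe, lasting either up to 7 days or longer. There are 10 pair types.

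| Pair | Severe count (needs 2) | Prolonged moderate count (needs 2) | Count-based stop |
|---|---|---|---|
| moderate >7 d + moderate >7 d | 0 | 2 | yes, criterion 4 |
| severe + severe (three duration combinations) | 2 | 0 | yes, criterion 3 |
| **moderate >7 d + severe >7 d** | **1** | **1** | **no** |
| moderate >7 d + severe ≤7 d | 1 | 1 | no |
| moderate ≤7 d + severe (two durations) | 1 | 0 | no |
| moderate ≤7 d + moderate (two durations) | 0 | 0 or 1 | no |

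The bold row is the only non-stopping pair that is at least as severe and at least as long as a stopping pair, namely the first row.

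The other criteria close the gap only in part:

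- Criterion 2 applies if the severe AE is serious, but Section 6.2.1.1.2 confirms that it need not be.
- The AE part of criterion 5 needs severe AEs in two subjects. Its other part applies only if the two events are similar laboratory, ECG or vital sign abnormalities.
- Because a grade change is recorded as a new AE, a severe AE that steps down to moderate for over 7 days would count under criterion 4. The gap therefore needs a severe AE without such a phase.

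**2. Size, for illustration only.** All rates are assumed and are per subject:

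- *s*: related severe AE
- *h*: share of those that are serious
- *f*: share of the non-serious severe AEs that last over 7 days without a moderate phase over 7 days
- *m*: related moderate AE over 7 days as the worst event

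With *n* subjects, the uncovered case is exactly one subject of each type and none of the others affected:

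gap = *n*(*n*−1) · *s*(1−*h*)*f* · *m* · (1−*s*−*m*)^(*n*−2)

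Example with *n*=8, *s*=0.05, *m*=0.10, *f*=0.5, *h*=0: 8 × 7 × 0.05 × 0.5 × 0.10 × 0.85^6 = 0.14 × 0.377 = 0.0528. Full multinomial enumeration gives the same value.

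| *s*, *m* | Gap, *n*=8 | Gap, *n*=6 (no such events on placebo) |
|---|---|---|
| 0.01, 0.03 | 0.05% to 0.66% | 0.03% to 0.38% |
| 0.02, 0.05 | 0.14% to 1.8% | 0.09% to 1.1% |
| 0.05, 0.10 | 0.42% to 5.3% | 0.31% to 3.9% |

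In each cell the low end is *f*=0.2, *h*=0.8 and the high end is *f*=0.5, *h*=0. These are not bounds. If every severe AE were non-serious and prolonged (*f*=1, *h*=0), the last *n*=6 entry would be 7.8%. Criterion 5 is not modelled and would lower the figures; replacement subjects (Section 4.4) could raise them.

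**The case against.** The strongest reply is that escalation is not automatic when no count is reached. Section 3.1 lets it proceed only once the prior cohort's safety and tolerability data are verified. Section 8.10 requires a review first, and SAP Section 7.3 highlights moderate, severe and related events in the review listing, so both AEs would be in plain view. Criterion 6 stands under the same mandatory heading. This stands in large part: a stop is likely. It is still a decision by the two parties and not a fixed consequence, whereas the milder pair leaves them no such choice.

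Criteria 3 and 4 also contain judgment, since the Principal Investigator decides relatedness and the Investigator assigns the grade. The override in criterion 5 turns on the same relatedness question. That is fair, and it narrows the contrast between firm and soft stops. Once those judgments are made, though, criteria 3 and 4 leave nothing further to decide.

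The case is also narrow. Subjects stay in the unit until Day 7, so a severe AE still present at discharge might prolong hospitalization, become serious and trigger criterion 2. Severe alopecia is only a definitional example and is not among the expected effects in Section 1.3. Both points make the gap rarer without removing it.

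Finally, the percentages depend on *f* and *h*, about which the documents say nothing. That is correct, and the finding does not rest on them.

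**Conclusion.** The concern holds as a minor inconsistency in the wording of a safety rule. Of the three grade pairings possible for two subjects with prolonged related AEs of moderate or severe grade, one (moderate plus severe) has no count-based stop although a milder one does.

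This rests on reading *moderate* as exactly that grade, on the severe AE being non-serious and without a moderate phase over 7 days, and on the two events not being similar laboratory, ECG or vital sign abnormalities. The true frequency is unknown and probably low; the ranges above only indicate scale. A discretionary backstop exists and would probably work. No endpoint or analysis is affected.

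**What to change.** In criterion 4 of Section 3.4, insert *or severe* after *moderate*, so that two subjects with related AEs of either grade lasting more than 7 days stop escalation. Of the 10 pair types, only the uncovered one changes. A brief severe AE together with a prolonged moderate one stays with the safety review.

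An optional clarification: state that time at moderate grade or above is counted continuously when a grade change opens a new AE record, since the text does not say how persistence is counted across records.

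The cost is a written amendment with IRB approval (Section 10.8) and a slightly higher chance of a mandatory stop. Under the assumed rates with *n*=8 and *h*=*f*=0.5, the chance of a stop under criteria 2 to 4 per cohort rises as follows:

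- *s*=0.01, *m*=0.03: 6.2% to 6.5%
- *s*=0.02, *m*=0.05: 13.3% to 14.3%
- *s*=0.05, *m*=0.10: 35.4% to 38.1%

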4. STUDY POPULATION

The study population will consist of healthy male and female volunteers. Subjects must be able to provide written informed consent and meet all the inclusion criteria and none of the exclusion criteria.

4.1. Number of Subjects

A total of approximately 40 subjects will be enrolled in the clinical study (N = 8 per cohort with 6 randomized to HM15912 and 2 randomized to matching placebo within each group) according to the inclusion/exclusion criteria. Enrolling 8 subjects per cohort (HM15912:placebo=6:2) has been set based on the experience and the general properties of exploratory studies, and this matches the typical sample size used in similar studies conducted to assess safety and PK. Therefore, no formal sample size calculation will be performed (refer to Section 8.11).

4.2. Inclusion Criteria

Subjects who meet the following criteria will be considered eligible to participate in the clinical study:

1. Subject voluntarily agrees to participate in this study and signs an IRB-approved informed consent prior to performing any of the Screening visit procedures.
2. Korean males and females ≥ 19 and ≤ 60 years of age at the Screening visit
3. Female subjects must be non-pregnant and non-lactating and either surgically sterile (e.g., bilateral tubal occlusion, hysterectomy, bilateral salpingectomy, bilateral oophorectomy), or post-menopausal for ≥ 12 months. Postmenopausal status will be confirmed through testing of follicle-stimulating hormone (FSH) levels ≥ 40 IU/L at the Screening visit for amenorrheic female subjects ≤ 60 years of age.

Male subjects must be surgically sterile (at least 1-year post vasectomy), abstinent or if engaged in sexual relations with women of child-bearing potential, the subject and his partner must be using the following acceptable effective or medically recognized dual protection contraceptive methods from the administration of IP to up to 60 days after receiving the dose of the IP.

- Effective contraceptive method: Sexual partner's surgical sterilization (e.g., bilateral tubal occlusion, hysterectomy, bilateral salpingectomy, bilateral oophorectomy), intrauterine contraception/device of the sexual partner
- Dual protection contraceptive method: Combinational use of physical barrier methods (male condom, female condom and diaphragm for the sexual partner, sponge, cervical cap), spermicide for females in the form of foam/gel/film/cream/suppository, oral or hormonal contraceptives for the sexual partner

The adequacy of other methods of contraception will be assessed on a case-by-case basis by the Principal Investigator.

4. Body mass index (BMI) ≥ 18.5 kg/m² and ≤ 27 kg/m² at the Screening visit and with a

weight \geq 50 kg for males and \geq 45 kg for females

5. Healthy, determined by pre-study medical evaluation (medical history, physical examination, vital signs, 12-lead ECG and clinical laboratory evaluations)

